7.14 Clarification of Adverse Events Related to Study Procedures

Any untoward event that occurs from the beginning of the IUS insertion procedure until completion of insertion, or from the beginning of the removal procedure until the completion of removal, will be reported as an AE. Bleeding and cramping/pain occurring during IUS insertion or removal will be recorded on the IUS Insertion and Removal CRFs, as appropriate. Any other insertion or removal AEs should be recorded on the AE CRF with a causality assessment of “related to IUS procedure.” If any AE meets the definition of a Serious Adverse Event, even if it is recorded on the diary or Insertion or Removal CRF, it should also be reported on the AE and SAE CRFs and submitted to Sponsor.

7.15 Follow-up of Adverse Events and Serious Adverse Events

All AEs and SAEs must be followed through the 30 Day Safety Follow-up Visit, and any IUS or IUS procedure related AEs or SAEs followed until resolution, or until the condition stabilizes, or until all queries are resolved, or until the subject dies or is lost to follow-up (including withdrawal of consent). The Investigator is responsible to ensure that follow-up includes any supplemental investigations as may be indicated to elucidate as completely as practical the nature and/or causality of the AE/SAE. This may include additional laboratory tests or investigations, histopathologic examinations, or consultation with other health care professionals. Follow-up information should be submitted to the Sponsor in a timely manner as the information is obtained.

7.16 Clarification in Reporting of Deaths

All subject deaths (regardless of relationship to study drug) should be reported that occur from the beginning of study IUS insertion through 30 days after IUS discontinuation (or through the 30-Day Safety Follow-up Visit for expulsions of unknown date) while on study protocol up to

and including the follow-up visit. The information should be recorded on the Subject Death form and the SAE form.

Death is an outcome of an adverse event and not an adverse event in itself. All reports of subject death should include an adverse event term (other than “Death”) for the cause of the death. Since reporting of an SAE is required within 24 hours of discovery, Death can be reported as an initial event term and updated to the final diagnosis in a follow-up report. If an adverse event term is not provided, the Investigator will be queried to obtain the cause of death. Only in the rare occurrence that no verbatim description of an adverse event can be obtained from the investigative site will “Death – Unknown Cause” be used as the event term.

7.17 Post-Study Treatment Reporting Requirements

For all enrolled subjects, all AEs and SAEs, regardless of cause or relationship, that occur from the beginning of study IUS insertion through 30 days after IUS discontinuation (through the 30-Day Safety Follow-up Visit for expulsions of unknown date) require reporting to the Sponsor. In addition, if the Investigator learns of any SAE at any time after a subject has discontinued study drug, and such event seems reasonably related to study drug, the Investigator should promptly notify the Sponsor.

7.18 Subject Withdrawal

7.18.1 Criteria for Withdrawal of Subject from Treatment

The following criteria will be used to determine when a subject should be withdrawn from treatment (removal of study IUS). Withdrawal from treatment is not the same as withdrawal from the study, and all subsequent study-related activities described in Sections 6.5 and 6.6 should be completed.

- Subjects may choose to discontinue IUS use at any time during the study
- Subjects who become pregnant during study participation will have the IUS removed. Subjects who become pregnant during study treatment will continue to be followed until pregnancy completion or termination to determine health-related outcomes of the pregnancy. The Investigator will provide pregnancy outcome information as a follow up to the initial pregnancy reporting form

- When IUS perforation occurs during insertion or while on treatment, the IUS will be removed and the subject will be discontinued
- Subjects who experience IUS expulsion (partial or complete)
- The Investigator or Sponsor may discontinue a subject from treatment for other reasons. These may include, but are not limited to, the following:
 - Noncompliance with return visit schedule, diary completion, or use of an excluded therapy
 - A clinically significant IUS-related adverse event or the development of a new significant medical condition that compromises the subject's ability to participate in the study
 - Investigator determination that it is not in the subject's best interest to continue participation
 - If the subject uses another form of contraception for four consecutive months, or establishes a pattern of intermittent use of other contraception for 4 months out of any 12 month period, the Medical Monitor should be contacted to discuss the subject's continuing participation in the study
- Subjects who have their IUS discontinued should be seen for the 30-Day Safety Follow-up visit unless the expulsion occurred 30 or more days prior, in which case the 30-Day Safety Follow-up visit may be combined with the Early Discontinuation visit

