APPENDIX B: MANAGEMENT OF PREGNANCY

Among women who conceive with an IUS *in situ*, the spontaneous abortion rate is two-fold higher than that of the general obstetric population. A retained IUS also increases the risk of several late gestational adverse maternal and neonatal outcomes; this risk is reduced, but not eliminated, with early removal of the IUS.

For any subject who has a positive urine pregnancy test, the pregnancy should be confirmed by ultrasonography and serum hCG testing. The location of the pregnancy must be determined (intrauterine or extrauterine) using ultrasonography. Determine the location of the IUS using physical examination, ultrasonography and/or radiography as appropriate.

1. Management of intrauterine pregnancy with IUS in place

The following steps may be considered in the evaluation and management of intrauterine pregnancy in a subject with an IUS *in situ*:

- First trimester intrauterine pregnancy:
 - If the IUS strings are visible on speculum examination, remove the IUS to decrease the risk of subsequent miscarriage and infection. Antibiotics are unnecessary.
 - If the strings are not visible and the patient wishes to continue the pregnancy, remove the IUS under ultrasound guidance using an alligator forceps or an IUS hook. Removal can also be attempted by hysteroscopy. Data on hysteroscopic removal of IUS in early pregnancy are limited; therefore, it is not clear whether this technique poses greater or lesser risk of pregnancy loss than instrument removal under ultrasound guidance. Antibiotic prophylaxis is recommended when instrument removals are performed during pregnancy, including when IUS removal is to be followed by pregnancy termination (see below). The IUS may be left *in situ* if findings on ultrasound examination suggest removal will be difficult or disrupt the pregnancy (e.g., IUS embedded in the placenta or membranes).
 - If the woman desires pregnancy termination, IUS removal can be performed at the time of the termination. Manual or electric vacuum aspiration or an instrument such as an IUS hook, alligator forceps, ring forceps, or ovum forceps can be used to remove the IUS.

- In the setting of spontaneous abortion with IUS in place, it is recommended to remove the IUS and prescribe antibiotics (e.g., doxycycline 100 mg twice a day or ampicillin 500 mg four times a day for seven days).

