- Second trimester pregnancy: Counsel subject if the IUS remains *in situ*, that there is an increased risk of preterm labor and delivery (fourfold increase), second trimester fetal loss, and infection, but no proven increase in risk of birth defects. Removal of the IUS may cause rupture of membranes, bleeding, pregnancy loss, or fetal trauma; however, if the IUS is removed or expelled without complications, there is no increased risk of miscarriage.
 - Given this information, for pregnancies after 12 weeks, consider removing the IUS by pulling on the strings if the strings are visible and removal is unlikely to disrupt the placenta or membranes (based upon ultrasound localization of the IUS and placenta).
 - If the strings are not visible in the early second trimester, the IUS may be removed under ultrasound guidance if removal appears feasible, the IUS is not located behind the placenta, and it does not appear to be incorporated into the gestational sac. In particular, ultrasound guided removal is recommended in these cases if the IUS is in the lower uterine segment. If the IUS appears embedded in the placenta, located behind the placenta, or protrudes into the gestational sac, we suggest leaving the IUS *in situ*.
 - In the later second trimester, if the strings are not visible, the IUS should be left in place. The subject should be counseled that her risk of spontaneous abortion and premature delivery is increased relative to women whose IUSs may be easily removed.

2. Management of intrauterine pregnancy with extrauterine IUS

- If the IUS was expelled, the pregnancy should be managed as any other intrauterine pregnancy.
If the IUS is extrauterine (perforation), the pregnancy should be managed without removal of the IUS until after the pregnancy is complete or, if applicable, at the time of cesarean section.

3. Management of extrauterine pregnancy

- Management should be performed within the local standard of care for the extrauterine pregnancy.
- If the IUS is intrauterine, the IUS should be removed and the subject discontinued from the study following appropriate safety follow-up.

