APPENDIX C: MANAGEMENT OF IUS ISSUES

1. Difficult Insertion

If insertion is difficult because the cervix cannot be properly visualized then the subject should have been excluded prior to randomization.

- If insertion is difficult because the uterus cannot be instrumented, the following measures are allowed:
 - Use of cervical anesthesia to make sounding and manipulation more tolerable
 - Use of Pratt dilators to dilate the cervix if needed to allow passage of the sound. If needed, a lacrimal duct probe or os finder may be used to start dilation but no other types of dilators are permitted.
 - Abdominal ultrasound guidance during dilation and/or insertion.

If the uterus still cannot be appropriately instrumented after the above measures are taken, or the uterus sounds to less than 5.5cm, then the subject should be considered an insertion failure and discontinued from the study. No further follow-up or visits are required.

2. Perforation

- Perforation may occur during insertion. The risk of perforation is increased in women with fixed retroverted uteri, during lactation, and postpartum. If during or after insertion there is clinical concern or exceptional pain or bleeding, appropriate and timely measures and assessments, such as ultrasound, should be performed to exclude perforation.
- Perforation or penetration of the uterine wall or cervix may occur during insertion although the perforation may not be detected until sometime later. The IUS must be located and removed; surgery may be required. Delayed detection of perforation may result in migration outside the uterine cavity, adhesions, peritonitis, intestinal perforations, intestinal obstruction, abscesses and erosion of adjacent viscera. Ensure a radiographic image of the entire abdomen is obtained to ensure the IUS hasn't migrated.
- If recognized and the IUS is intra-abdominal, a laparoscopy should be performed by a clinician experienced in such procedures to remove the IUS. Typically, minimal adhesions are present with intra-abdominal IUSs. If necessary, a laparotomy should be performed.

If the IUS is partially into or through the myometrium, it is reasonable to attempt removal with transcervical instrumentation. Initial attempts should be performed under ultrasound guidance using an Alligator forceps (or similar instrument). If unsuccessful, attempts via hysteroscopy should be made before proceeding to laparoscopy.

3. Missing Strings

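### Protocol 7.18.1 orders IUS removal in pregnancy and after perforation without exception, while Appendix B leaves the IUS in place or defers removal in four pregnancy situations, and no text says which governs

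*Protocol*

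**What the plan says.** Protocol 7.18.1 lists the criteria for withdrawing a subject from treatment and equates withdrawal with taking the study IUS out. On pregnancy it says "Subjects who become pregnant during study participation will have the IUS removed". On perforation it says "When IUS perforation occurs during insertion or while on treatment, the IUS will be removed and the subject will be discontinued". Neither sentence has an exception, and neither refers to Appendix B.

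Appendix B, which covers pregnancy management, describes four situations in which the IUS is not removed, or not yet:

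- First trimester, strings not visible: the IUS may stay "if findings on ultrasound examination suggest removal will be difficult or disrupt the pregnancy".
- Early second trimester, strings not visible, with the IUS embedded in the placenta, behind it, "or protrudes into the gestational sac, we suggest leaving the IUS" in situ.
- Later second trimester: "In the later second trimester, if the strings are not visible, the IUS should be left in place".
- Intrauterine pregnancy with a perforated IUS: "If the IUS is extrauterine (perforation), the pregnancy should be managed without removal of the IUS until after the pregnancy is complete" or, where it applies, until cesarean section.

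Appendix C, on perforation in general, says "The IUS must be located and removed; surgery may be required" and does not mention pregnancy.

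Two other sections bear on this. Section 7.1.1 says a pregnant subject will be told that the device ought to come out, qualified by standard medical care, and then refers to Appendix B. Section 7.4 also refers to Appendix B.

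**The concern.** For some pregnant women, a site that reads 7.18.1 and a site that reads Appendix B would plan different actions, and nothing in the protocol ranks the two texts. Appendix B itself describes risks on both sides for the second trimester: removal can rupture membranes or cause bleeding, pregnancy loss or fetal trauma, and a retained device raises the risk of preterm delivery, fetal loss and infection. The instruction therefore needs to be unambiguous.

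There is also a data question. AE and SAE reporting (Protocol 7.7, 7.10, 7.12 and 7.17) runs to 30 days after IUS discontinuation. The safety visit in 6.7 is timed from the Treatment Completion/Early Discontinuation Visit, at which 6.6 lists removal of any IUS not already out. If the device stays in for months under Appendix B, the protocol does not say when either clock starts.

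**Working it through.** This is a comparison of texts; the plan gives no figure to reproduce.

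**Step 1. Set the rules side by side.**

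| Situation | 7.18.1 | Appendix B | Strength of Appendix B wording |
|---|---|---|---|
| First trimester, strings not visible, removal difficult or disruptive | Remove | May stay | Permissive |
| Early second trimester, strings not visible, IUS in or behind placenta or in sac | Remove | Leave | Suggestion |
| Later second trimester, strings not visible | Remove | Leave | *Should* |
| Intrauterine pregnancy with perforated IUS | Remove and discontinue | Defer removal to end of pregnancy or cesarean section | *Should* |

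Four situations depart from the unconditional wording of 7.18.1, and two of them are worded *should*. The first three fall under Appendix B item 1, which is introduced as steps to consider. The perforation rule is in item 2, outside that introduction.

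**Step 2. Check where the texts agree.** Appendix B also calls for removal in the first trimester with visible strings, and in extrauterine pregnancy with the IUS in the uterus. Both match 7.18.1. Appendix C matches 7.18.1 on perforation because it does not address pregnancy.

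**Step 3. Look for a ruling text.** Sections 7.1.1 and 7.4 direct the reader to Appendix B; 7.18.1 does not. No passage says that Appendix B qualifies 7.18.1, or the reverse.

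**Step 4. Follow the dates.**

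- *Pearl Index.* For a subject who becomes pregnant with the IUS in place, SAP 5.4 sets the last date of use at the estimated conception date. Exposure ends there whether the device is later removed or kept.
- *Pregnancy outcome.* Protocol 7.4 and 7.18.1 follow on-treatment pregnancies to completion, so this does not depend on removal either.
- *AE/SAE reporting and the 30-day visit.* These depend on IUS discontinuation and on the discontinuation visit. Neither date is defined for a retained IUS.
- *Adverse event tables.* The SAP counts treatment-emergent events in discontinued subjects to 30 days after last known use, which under SAP 5.4 is conception plus 30 days. The span reported by sites and the span tabulated could therefore differ.

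**Step 5. Ask how many women.** Sample-size inputs (Protocol 9.1, SAP 4): 1,600 LNG20 women; a Pearl Index below 0.280; yearly discontinuation of at most 20%, 19%, 17%, then 16%; month losses of 0.6 in year 1 and 0.3 a year after that. Woman-years per year = average of women at start and end − (months lost ÷ 12) × women at start.

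- Year 1: (1,600 + 1,280)/2 − 0.05 × 1,600 = 1,360. Over ten years the sum is 6,802, and 0.0028 × 6,802 = 19 pregnancies.
- If the yearly losses are scaled down (on the log-survival scale) to match the stated 76% cumulative figure, exposure is 8,005, and 0.0028 × 8,005 = 22.

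These are all pregnancies at a rate the plan expects not to reach. They include ectopics, pregnancies after unrecognized expulsion, and first-trimester cases with visible strings, where the conflict does not arise. Protocol 7.1.5 puts perforation at about 1 per 1,000 insertions, or 1,600/1,000 = 1.6 women, before requiring a pregnancy as well. The documents give no figure for the share in the four rows above.

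**The case against.** The best reply is that 7.18.1 is a list of withdrawal criteria and not the pregnancy-management section. Sites are sent to Appendix B twice, by 7.1.1 and by 7.4, and a careful investigator would treat it as the detailed rule. Much of Appendix B is advisory, so it may be read as leaving room for judgement. On this view 7.18.1 merely lacks a cross-reference.

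Part of this stands. The pointers make a wrong reading less likely, and only two of the four situations use *should*. But 7.18.1 is worded as mandatory and carries no pointer. The advisory introduction to Appendix B item 1 makes it harder, not easier, to read as overriding a mandatory sentence.

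On perforation the reply is stronger. Neither 7.18.1 nor Appendix C sets a deadline for removal, and Appendix B postpones it without cancelling it. A reader might infer that the three texts cannot all be followed. The documents do not support that for perforation, where the question is when, and only if the woman is pregnant.

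A reader might also infer that conflicting end-of-treatment dates would disturb the efficacy estimate. They should not, given the conception-date rule in SAP 5.4.

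**Conclusion.** The inconsistency is real and in the current text. Protocol 7.18.1 is unconditional, Appendix B departs from it in four situations, 7.1.1 offers a third wording, and nothing says which prevails. It bears on the safety of individual women and is worth correcting for that reason. No position is taken here on which clinical instruction is right.

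The statistical consequence is narrow. The primary and key secondary Pearl Indices should be unaffected. This assumes that the conception-date rule is applied to every pregnancy with the IUS in place, including when a removal date is recorded later; SAP 5.4 lists the rule among cases with an unknown removal or expulsion date. What stays open is the start of the protocol's AE/SAE window and of the 30-day visit for a retained IUS.

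The number affected is small but cannot be estimated. The 19 to 22 pregnancies from the planning rate might be taken as the size of the problem; they are a planning ceiling for all pregnancies and do not count the conflicting cases.

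**What to change.** - Reconcile 7.18.1, 7.1.1, Appendix B and Appendix C so that one rule covers pregnancy with the IUS in place and one covers pregnancy with a perforated IUS. The sponsor's medical team should decide the clinical content.
- Make 7.18.1 refer to that rule, and state which text governs if a difference remains.
- State which date counts as IUS discontinuation for AE/SAE reporting and for the 30-day safety visit when the IUS is retained, consistent with SAP 5.4. If the reporting date is meant to differ from the SAP's last-use date, say so in both documents.

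The cost is protocol wording in an amendment or administrative letter, with a matching line in the SAP if needed. No procedures, visits or subjects are added, and the efficacy analysis does not change.

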7.18.2 Withdrawal from the Study

The following criteria will be used to determine when a subject should be withdrawn from the study:

- A subject may withdraw consent for further participation in the study at any time without giving a reason
- Any subject for whom correct insertion of the assigned IUS is not successful will be withdrawn from the study without further testing or follow-up (except in the case of IUS insertion procedure-related adverse events which should be appropriately assessed and followed as per Section 7.12)

- A subject may choose to stop participation in the study for any reason. If the subject has not withdrawn consent and has an IUS in place they should be brought in for IUS removal and Early Discontinuation procedures with appropriate 30-Day Safety Follow-up Visit
- A subject may also be discontinued from the study at the request of the Investigator or the Sponsor. If the subject has an IUS in place they should be brought in for removal and Early Discontinuation procedures with appropriate 30-Day Safety Follow-up Visit
- A subject may be discontinued from the study if she relocates to a residence greater than approximately 150 miles from the original study site. The subject may request to be transferred to another study site within 150 miles of her new location (if available). Each request for transfer or discontinuation due to relocation should be reviewed with the Medical Monitor. Any subject being discontinued due to relocation should undergo Early Discontinuation procedures with appropriate 30-Day Safety Follow-up Visit
- Sponsor decision to terminate the study or discontinue the investigative site's participation

Reasons for subject withdrawal from the study should be documented in the subject's file and entered into the CRF.

Subjects that are designated as withdrawn from the study, lost to follow-up or who withdraw consent may not re-enter the study.

7.18.3 Screen Failures

A Screen Failure is defined as any subject that has given consent to participate in the study (i.e. signed an Informed Consent Form) and subsequently was not randomized or enrolled into the study.

7.18.4 Missed Visits/Contacts and Lost to Follow Up

All reasonable efforts should be made to ensure that enrolled subjects return to the investigational site for all study visits. Any subject who misses a scheduled visit or telephone follow-up call should have further contact attempts by the study staff as follows:

- At least three documented attempts to contact the subject by phone, e-mail or similar mode of communication

- If the subject cannot be contacted, or is contacted and still fails to come in for a scheduled visit, a certified letter must be sent to the subject indicating the importance of follow-up and instructed to contact the site immediately
- If subject contact is unsuccessful then future attempts should be made at the time of the next expected study contacts (visits or telephone contact)
 - At least three documented attempts to contact the subject by phone, e-mail or similar mode of communication should be completed
 - If the subject cannot be contacted, or is successfully contacted but still fails to be seen for a scheduled study visit, a certified letter must be sent to the subject indicating the importance of follow-up and should be instructed to contact the site immediately. The letter should indicate that failure to reply within 30 days of the letter date will result in study discontinuation and no future study-related activities will be provided. Certified letters do not need to be sent for subsequent missed study visits if a previous delivery attempt was unsuccessful (letter returned or accepted with no subsequent response)

A subject should be considered lost to follow-up when:

- Scheduled study visits or phone contacts are missed for at least 6 months, spanning from the last study contact to the end of the window for the next scheduled visit or phone contact. A subject may be considered lost to follow up after missing two consecutive clinic visits, even if she has been compliant in completing her phone contacts per the protocol
- The 30-Day Safety Follow-up Visit is missed and three documented contacts and a certified letter do not result in a study visit within 30 days of the end of the expected visit window

Subjects designated as lost to follow-up who later resume contact with the site should be requested to have their IUS removed but no other study-related procedures are to be conducted and no study documentation other than IUS accountability is required but clinical documentation of the IUS removal should be made.

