- Removal of IUS, if not already expelled or removed (at an outside location)
- Retain all removed or expelled IUSs (when possible) per the Study Reference Manual
- Contraceptive counseling
 - Immediate initiation of another method in the office when possible
 - Request to use this method or be abstinent for at least one week to avoid conception within 7 days after IUS discontinuation
- Schedule next appointment

6.7 30-Day Safety Follow-Up

All subjects must have a safety follow-up visit between 30 and 43 days after the Treatment

Completion/Early Discontinuation Visit (except those made lost to follow up or who withdrew consent per section 7.18). If the subject contacts the office with an expulsion that was 30 or more days ago, this visit may be combined with the Early Discontinuation visit.

- Review of adverse events (note: all adverse events occurring within 30 days of IUS discontinuation should be reported on the appropriate adverse event CRF)
- Review of concomitant medications used up to 30 days of IUS discontinuation
- Menstrual history if not using a hormonal method of contraception
- High sensitivity urine pregnancy test (if positive, see Sections 7.4 and 7.5)
- Weight and blood pressure
- Additional contraceptive counseling if needed
- Review with subject that continued telephone or clinic follow-up (as appropriate) is indicated for the following:
 - an ongoing IUS-related adverse event at study discontinuation should be followed monthly until the adverse event resolves or has stabilized
 - any subject electing to use a non-hormonal contraceptive method or no contraception (including those desiring pregnancy) will be followed monthly for up to 3 months after IUS removal/expulsion for return of menses. Any woman who does not menstruate within 3 months following IUS discontinuation will be referred for appropriate evaluation and continue to be followed monthly until menses has occurred or a diagnosis for the cause of the secondary amenorrhea has been established
- Those women desiring a pregnancy after IUS discontinuation will be contacted every three months from their Treatment Completion/Early Discontinuation Visit up to one year to record return to fertility.
 - Once a pregnancy is reported no further follow-up contact is required.
 - Women who do not become pregnant and change their intention before completing a full 12 months of follow-up will be discontinued from the study and not be included in the return to fertility cohort.

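### Protocol 7.18.4 tells sites they need not test, or record events in, a lost-to-follow-up woman who returns with the IUS in place, contradicting the protocol's own AE, SAE and pregnancy reporting rules

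*Protocol*

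**What the plan says.** Protocol 7.18.4 gives two routes to lost-to-follow-up status during treatment. One is a gap in contact: "Scheduled study visits or phone contacts are missed for at least 6 months". The other is discretionary: a woman may be designated lost "after missing two consecutive clinic visits, even if she has been compliant in completing her phone contacts". Protocol 7.18.2 makes the status final: "Subjects that are designated as withdrawn from the study, lost to follow-up or who withdraw consent may not re-enter the study".

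If she later resumes contact, 7.18.4 has the site request removal of the IUS, and beyond that "no other study-related procedures are to be conducted and no study documentation other than IUS accountability is required". The one addition is that "clinical documentation of the IUS removal should be made", which is a clinical record and not study data. Protocol 6.7 also excuses her from the 30-day safety visit ("except those made lost to follow up or who withdrew consent per section 7.18").

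The reporting sections are written differently. Protocol 7.17 begins "For all enrolled subjects, all AEs and SAEs, regardless of cause or relationship" and runs from insertion to 30 days after IUS discontinuation. Protocol 7.10 sets the same window for SAEs. Protocol 7.1.1 and 7.4 require pregnancies on the IUS to be followed to completion, and 7.5 lists the forms to complete. SAP 9.1 requires an investigator narrative for every reported pregnancy, confirmed or not.

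**The concern.** The reporting windows are tied to IUS discontinuation, not to the end of study participation. A woman who returns with the device in place has not discontinued it, so her events up to removal and for 30 days afterwards are reportable. Yet the section written for exactly her situation tells the site to do nothing further for the study and to record only the device.

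At stake are the completeness of pregnancy and AE ascertainment in a single-arm efficacy assessment, and consistency across up to 30 sites. The IDMC reviews pregnancy rates and safety data, and Protocol 9.9 has a stopping rule on the pregnancy rate. Both depend on sites applying one rule.

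**Working it through.** The plan states no figure for this point, so the check is mainly a comparison of sections. The arithmetic only bounds the size.

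**1. What each section requires for a lost woman who returns with the IUS in place**

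| Item | Reporting sections | 7.18.4 |
|---|---|---|
| Urine pregnancy test | 6.6: done at early discontinuation | No other study procedure |
| AE review | 6.6: done at early discontinuation | No other study procedure |
| AE and SAE forms | 7.10, 7.17: through 30 days after IUS discontinuation | Not required |
| Pregnancy forms and narrative | 7.5, SAP 9.1 | Not required |

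The two halves of the clause differ. On procedures it prohibits. On documentation it only waives.

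**2. Comparison with other departures.** Under 7.18.2, a woman who stops participation without withdrawing consent, relocates, or is discontinued by the investigator or sponsor undergoes the Early Discontinuation procedures, including the pregnancy test and AE review. Under 7.18.5 even a woman withdrawing consent is asked to attend that visit. A lost woman who never withdrew consent gets less.

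**3. Length of the untested gap.** By the contact-gap route it is at least 6 months. By the clinic-visit route, visits after Month 6 are six months apart, so two consecutive misses put her last scheduled test about 6 + 6 = 12 months back. The telephone contacts in 6.5 include AE review but no pregnancy test.

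**4. What happens to the exposure.** SAP 10.2.2 censors the life table at the last pregnancy assessment. SAP 5.5 takes the smaller of the date-based and diary-based cycle counts, so a gap without diaries drops out of the primary Pearl Index. Numerator and denominator therefore largely lose the gap together. Bias arises only to the extent that loss or return is related to pregnancy. One loose end is that SAP 5.4 uses a known removal date, whereas its last-pregnancy-test rule is written for women still on treatment. The SAP does not say which applies to a removal after designation.

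**5. Expected unobserved pregnancies.** Inputs from the documents are 1,600 women and a Pearl Index ceiling of 0.280 per 100 woman-years (Protocol 9.1). Assumed, because not given: 5–20% lost, 10–50% of those returning, and a gap of 0.5–2 years.

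- Formula: 1,600 × lost share × return share × gap × 0.0028
- Low: 1,600 × 0.05 × 0.10 × 0.5 = 4 woman-years; × 0.0028 = 0.01 pregnancies
- High: 1,600 × 0.20 × 0.50 × 2 = 320 woman-years; × 0.0028 = 0.9 pregnancies

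These assume that loss and return are unrelated to pregnancy. If they are related, the number is higher.

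**6. Weight of one pregnancy in the primary index.** Exposure is taken at the plan's discontinuation ceilings (20% in year 1, 19% in year 2), with departures at mid-year and the stated lost months.

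- Year 1: (1,600 + 1,280)/2 × (12 − 0.6)/12 = 1,368 woman-years; 100/1,368 = 0.07
- Year 2: (1,280 + 1,036.8)/2 × (12 − 0.3)/12 = 1,129 woman-years; 100/1,129 = 0.09

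With exact Poisson limits (assumed) in year 1, the distance from estimate to upper limit is 0.38 with two pregnancies and 0.42 with three. Both are well inside the 1-unit criterion. In year 10, at the 350 woman-years stated in Protocol 9.1, one pregnancy is worth 100/350 = 0.29. These are weights of a single event, not estimates of bias.

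**The case against.** The best defence is that 7.18.4 does not override the other sections. It says further documentation is not required, which is not a ban. A site that learns of an SAE must still report it under 7.10 and 7.17, and 7.17 adds later SAEs that seem reasonably related. A woman who returns saying she is pregnant is a reported pregnancy under SAP 9.1. This stands. A reader might infer that pregnancies and serious harms in these women go unrecorded and never reach the sponsor or IDMC; the documents do not support that.

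A reader might also set one missed pregnancy against the total expected over ten years, or against a single late year, and call the result the bias. That does not follow, because the unobserved time largely leaves the denominator too and 0.280 is a ceiling. Nor do the documents show that women return because of pregnancy or complications. It is plausible, but it is an assumption.

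Finally, the sponsor could say that loss to follow-up ends study data collection, pointing to the bar on re-entry, the 6.7 exemption, and 7.15, which stops following known events at loss. This answers only part of the point. Those sections show that the protocol writes the exception where it wants one. The sections on reporting new events and pregnancies contain none, and 7.17 applies to all enrolled subjects.

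**Conclusion.** The point holds as an internal contradiction with a real but narrow consequence. Section 7.18.4 excludes a study pregnancy test and AE review at the return contact and waives records that 7.5, 7.10, 7.17 and SAP 9.1 require. What can be lost is mainly pregnancies nobody has yet detected and non-serious AEs. What becomes inconsistent is the recording of events that are known, since sites can point to different sections.

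Any error is toward fewer events. Its size cannot be derived from the documents. Under the assumed ranges it is 0.01 to 0.9 expected pregnancies over the whole trial, and more if loss or return is related to pregnancy. The year 1 and year 2 primary result is probably little affected. The point matters more for safety reporting and for later years, where exposure is small. It deserves correction but does not put the primary analysis in doubt.

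**What to change.** **Protocol.** Reconcile 7.18.4 with 7.4, 7.5, 7.10 and 7.17. For a returning woman who has not withdrawn consent, apply the urine pregnancy test and AE review already listed in 6.6 at the removal contact. Complete the existing pregnancy, AE and SAE forms for events through the reporting window. Because 6.7 exempts her from the 30-day visit, state how events in the 30 days after removal are to be captured. Who may be designated lost need not change.

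**SAP.** List these events separately in the safety tables. State whether a conception after designation with the IUS in place counts as on-treatment under 9.1, and whether a late removal date extends exposure under 5.4 and 5.5. If such conceptions enter a sensitivity Pearl Index, include the matching gap exposure; otherwise the index would count events without the time at risk that produced them. The primary index can stay as it is.

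**Cost.** Amended wording, one urine test of a kind already in use, and existing forms for the women who return. IUS accountability records and clinical removal notes could help identify earlier returns. The drawback is late, recall-based data from a self-selected group, so they suit listings and sensitivity analysis only.
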